8.2 Banking of Leftover Biospecimens

Subject consent will be obtained to bank any leftover samples that were collected for study-specific correlative research. Hoosier Cancer Research Network (HCRN), as Administrative Headquarters for the Big Ten CRC, will manage the banked samples. Samples will be banked indefinitely in the Hoosier Cancer Research Network Biorepository and used for future unspecified cancer-related research.

8.3 Banking Samples for Future Unspecified Research

Subject consent will be obtained to collect additional samples for future unspecified Big Ten Cancer Research Consortium studies. HCRN will manage the banked samples. Samples will be banked indefinitely in the HCRN Biorepository.

This includes:

- Whole blood: Whole blood will be collected prior to treatment on Cycle 1 Day 1.
- Pre- and Post-treatment plasma: Whole blood for plasma will be collected prior to treatment on Cycle 1 Day 1 and at the 30-day Safety Follow-up visit.
- Pre- and Post-treatment serum: Whole blood for serum will be collected prior to treatment on Cycle 1 Day 1 and at the 30-day Safety Follow-up visit.
- Unstained slides: Unstained slides will be obtained from the subject's archived pre-treatment formalin fixed paraffin embedded prostate tumor tissue sample and also from the prostatectomy sample, when applicable.

Please refer to the Correlative Laboratory Manual (CLM) for all sample collection, processing, labeling, and shipping instructions.

8.4 Confidentiality of Biospecimens

Samples will be identified by a subject's study number assigned at the time of registration to the trial. Any material issued to collaborating researchers will be anonymized and only identified by the subject's study number.

9. CRITERIA FOR DISEASE EVALUATION

9.1 Phase II Neoadjuvant cohort

9.1.1 Pathological response

Response for the Phase II neoadjuvant cohort will be evaluated at the time of prostatectomy. Those with pathological complete response (absence of pathologic disease on hematoxylin and eosin (H&E) stain (defined as ypT0)), or with presence of minimal residual disease (<5 mm linearly), will be considered to be responders. Those with more than minimal residual disease will be considered to have no response.

9.1.2 Biochemical recurrence

Relapse or recurrence will be determined by detectable PSA (≥ 0.1 ng/mL) on scheduled bloodwork confirmed with a rising PSA at least one week later, the appearance of metastatic disease on imaging, or biopsy-proven relapse. For biochemical recurrence, the date of recurrence will be dated back to the initial detectable PSA.

9.1.3 PSA_0

PSA_0 is defined as recovery of testosterone to non-castrate level (>50 ng/dL) and undetectable PSA (reported as ≤ 0.1 ng/mL or undetectable).

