2.2.2 Secondary Endpoints

- Grade 3 and 4 toxicities as defined by the NCI Common Terminology Criteria for Adverse Events (NCI CTCAE) v5.
- Two year biochemical recurrence-free survival (PSA ≤ 0.2 ng/mL)
- Rate of PSA₀ (undetectable PSA on local institutions laboratory testing with testosterone recovery and no additional therapy)

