12.2.2 Definition of Secondary Endpoints

- Grade 3 and 4 toxicities as defined by the NCI Common Terminology Criteria for Adverse Events (NCI CTCAE) v5.
- Two year biochemical recurrence-free survival (defined as PSA \leq 0.2 ng/mL)
- Rate of PSA₀ (undetectable PSA on local institutions laboratory testing with testosterone recovery and no additional therapy)

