12.6.2 Analysis Plans for Secondary Objectives

For secondary endpoints, descriptive statistics will be given for rates of toxicity and rates of PSA₀. Kaplan-Meier methodology will be used to estimate BCR-free survival, with 95% confidence envelope around the survival curve.

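### PSA₀ is defined inconsistently: a PSA of exactly 0.1 ng/mL is both undetectable (9.1.3) and detectable (9.1.2), and 2.2.2 and 12.2.2 use a different, site-dependent rule

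*Combined protocol and SAP*

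**What the plan says.** Three sets of sections in the combined protocol and SAP bear on this point.

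- **Section 9.1.3** gives the only numeric rule. The testosterone part reads "PSA_0 is defined as recovery of testosterone to non-castrate level (>50 ng/dL"; the PSA part reads "and undetectable PSA (reported as ≤ 0.1 ng/mL or undetectable". It does not mention further treatment.
- **Section 9.1.2**, directly above it, bases recurrence on "detectable PSA (≥ 0.1 ng/mL) on scheduled bloodwork confirmed with a rising PSA at least one week later". For a biochemical recurrence, "the date of recurrence will be dated back to the initial detectable PSA".
- **Sections 2.2.2 and 12.2.2** define the PSA₀ endpoint as "undetectable PSA on local institutions laboratory testing with testosterone recovery and no additional therapy". They give no PSA cut-off. The synopsis, 2.1.2 and 12.6 carry a shorter form, also without a number, and also require that no additional therapy was given.

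The companion endpoint in 2.2.2 is "Two year biochemical recurrence-free survival (PSA ≤ 0.2 ng/mL", a third PSA threshold. For PSA₀, section 12.6.2 plans no test: "descriptive statistics will be given for rates of toxicity and rates of PSA₀". None of these sections says when PSA₀ is assessed. Section 7.2 sets follow-up every 6 months for two years after prostatectomy or until biochemical recurrence, and the Phase II calendar has PSA and testosterone measured at those visits.

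**The concern.** PSA₀ and biochemical recurrence are the two post-operative efficacy outcomes, and both are read from the same blood samples. One would expect a sample that counts as a PSA₀ success not to mark the start of a recurrence as well. The text allows this at 0.1 ng/mL.

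The trial also runs at several institutions (13.1 refers to calls with all of them). If undetectable means whatever the local laboratory reports as undetectable, the PSA₀ rate depends partly on which assay each site uses. If it means the fixed ceiling in 9.1.3, it does not. The plan does not say which rule governs.

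Because PSA₀ is reported only descriptively, the definition determines the whole result. Leaving the choice until the data are in would let it be made with the outcomes known.

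**Working it through.** **Inputs.** Undetectable: PSA ≤0.1 (9.1.3). Detectable: PSA ≥0.1 (9.1.2). Recurrence-free: PSA ≤0.2 (2.2.2, 12.2.2). Phase II size: 17 evaluable, 20 enrolled (12.3). The plan gives no expected PSA₀ rate, precision or denominator, so there is no PSA₀ figure to reproduce.

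**Step 1. Fixed thresholds side by side (ng/mL).**

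| PSA | Undetectable, 9.1.3 | Detectable, 9.1.2 | Within ≤0.2, 2.2.2/12.2.2 |
|---|---|---|---|
| 0.09 | yes | no | yes |
| 0.10 | **yes** | **yes** | yes |
| 0.11 | no | yes | yes |
| 0.20 | no | yes | yes |
| 0.21 | no | yes | no |

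Sections 9.1.2 and 9.1.3 agree on either side of 0.10 and contradict each other only there. From 0.10 to 0.20 a man meets the recurrence-free threshold while 9.1.2 calls his PSA detectable.

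**Step 2. From 0.10 to a recurrence date.** One value of 0.10 is not a recurrence; 9.1.2 also needs a rise at least one week later. If the rise comes, recurrence is dated back to the 0.10 sample. If testosterone was above 50 ng/dL on that sample, 9.1.3 also makes it a PSA₀ success.

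**Step 3. Fixed ceiling against local limit.** Let L be a laboratory's reporting limit, with a result undetectable locally when PSA < L. The documents give no L, so the values below are assumptions. The two rules differ for L ≤ PSA ≤ 0.1.

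| Assumed L | Values below 0.1 on which 9.1.3 and 2.2.2/12.2.2 differ |
|---|---|
| 0.1 | none |
| 0.05 | 0.05 to 0.09 |
| 0.02 | 0.02 to 0.09 |
| 0.01 | 0.01 to 0.09 |

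**Step 4. Additional therapy.** A man with PSA ≤0.1 and recovered testosterone who has had further treatment is PSA₀ under 9.1.3 and not under 2.2.2 or 12.2.2, whatever the assay.

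**Step 5. Size.** One reclassified man moves the rate by 1/17 = 5.9 points or 1/20 = 5.0 points.

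**Step 6. Does the primary design depend on this?** Probability of success = Σ over x = 1 to 9 of P(X₁ = x) × P(X₂ ≥ 3 − x), with X₁ ~ Bin(9, p) and X₂ ~ Bin(8, p). At p = 0.05 this is 0.0466, within the stated 0.05; at p = 0.30 it is 0.9045, the stated 90.5%. Enrolment is 17/(1 − 0.15) = 20. The design reproduces and uses no PSA value.

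**The case against.** The strongest reply is that section 9 contains the disease-evaluation criteria, so 9.1.3 can be read as supplying the number for the shorter endpoint label: a local result reported as ≤0.1 or as undetectable counts as undetectable. On that reading a man at 0.05 is PSA₀ at every site, and 2.2.2 and 12.2.2 merely lack a cross-reference. This is reasonable, and it may be what was intended. But no section says so, and it removes neither the overlap at 0.1 nor the missing therapy condition.

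It can also be said that the overlap is a single value and that a stable 0.1 never becomes a biochemical recurrence under 9.1.2. Both are correct. The double classification needs a value of exactly 0.1, recovered testosterone and a confirmed rise. That need not be rare if a laboratory reports to one decimal, but the documents say nothing about assay precision.

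A reader might go further and infer that every low but measurable value, say 0.02 to 0.09 ng/mL, fails the endpoint definition while passing 9.1.3. The documents do not support that. The range appears nowhere in them, and step 3 shows that the conflict below 0.1 vanishes at a limit of 0.1 and is partial at 0.05.

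Finally, PSA₀ is secondary and descriptive, with no test or stopping rule attached. That limits the consequence but does not make the definitions agree.

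**Conclusion.** The point holds in limited form. Three things follow from the text alone: 0.1 ng/mL falls in both categories, 9.1.3 omits a condition that 2.2.2 and 12.2.2 require, and no assessment time is given. Different classification below 0.1 is conditional: it needs a site with a reporting limit under 0.1 and a reading in which the local rule governs.

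The size is 5.9 points per reclassified man if 17 are counted, or 5.0 if 20 are. How many men this involves is unknown and may be none, so a total shift of any particular size, which a reader might be tempted to project, has no basis in the documents. Nor should the point be read as casting doubt on the primary result: pathological response, type I error, power and sample size do not depend on it. It is a contradictory endpoint rule that should be settled before the outcomes are known.

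**What to change.** State one PSA₀ rule wherever PSA₀ is defined (2.2.2, 9.1.3, 12.2.2, and the matching text in the synopsis, 2.1.2 and 12.6): PSA <0.1 ng/mL or reported as undetectable, whatever the assay, with testosterone >50 ng/dL and no additional therapy. This does not overlap with the ≥0.1 in 9.1.2.

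Name one assessment visit from the existing 6-monthly schedule and count a man who recurred before it as not PSA₀. Twenty-four months is one reasonable choice, since it matches the two-year recurrence endpoint; other scheduled visits could be defended. The rule for men who recurred is needed because section 7.2 lets follow-up end at recurrence.

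In the same edit, reconcile the ≤0.2 ng/mL recurrence-free threshold in 2.2.2 and 12.2.2 (repeated in the synopsis and 2.1.2) with 9.1.2. The PSA₀ rule above stays clear of recurrence whichever threshold is kept.

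**Cost.** Wording only, with no added visits. Section 7.2 allows follow-up by telephone, so PSA and testosterone results must be on file for the named visit. The rate may be slightly lower than under 9.1.3 (men at exactly 0.1, men given further therapy, men who recur before the visit) or higher than under a strict local-limit reading (men between the local limit and 0.1). A laboratory whose reporting limit is above 0.1 would still be a source of site dependence; 9.1.2 already presupposes that 0.1 can be measured.

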9.2 Phase I De-escalation Cohort

Response will be evaluated in the Phase I Cohort at 12 weeks, using PCWG3 criteria. No additional timepoints for response evaluation are mandated, with the exception of those with bone-only progression requiring confirmation scan. For those without progression and continuing on therapy, tumor evaluation should occur at least annually. Patients will continue to be followed until the time of progression or end of treatment, whichever comes first. The timing (date) and cause (radiographic progression, clinical progression, PSA progression, toxicity) of end of treatment will be recorded. It is recommended that treatment continue until radiographic progression, but physician/designee discretion is allowed.

9.3 Prostate Cancer Working Group 3 (PCWG3) response criteria

This study makes use of a modified version of the PCWG3 response criteria for the Phase I cohort, which consists of the following three distinct evaluations, with separate evaluation for measurable disease (modified RECIST 1.1), bone metastases (2+2 rule), or PSA response. Please see below for details.

9.4 Measurable disease

Measurable disease is defined as the presence of at least one lesion that can be accurately measured in at least one dimension (longest diameter to be recorded) as ≥ 10 mm with CT scan. All tumor measurements must be recorded in millimeters (or decimal fractions of centimeters).

9.4.1 Malignant Lymph Nodes

To be considered pathologically enlarged and measurable, a lymph node must be ≥ 15 mm in short axis when assessed by CT scan (CT scan slice thickness recommended to be no greater than 5 mm). At baseline and in follow-up, only the short axis will be measured and followed.

9.5 Non-measurable Lesions

All other lesions (or sites of disease), including small lesions (longest diameter <10 mm or pathological lymph nodes with ≥ 10 to <15 mm short axis), are considered non-measurable disease. Bone lesions, leptomeningeal disease, ascites, pleural/pericardial effusions, lymphangitis cutis/pulmonitis, and abdominal masses (not followed by CT or MRI), are considered as non-measurable.

9.6 Target Lesions

All measurable lesions up to a maximum of 2 lesions per organ and 5 lesions in total, representative of all involved organs, should be identified as target lesions and recorded and measured at baseline. Target lesions should be selected on the basis of their size (lesions with the longest diameter), be representative of all involved organs, but in addition should be those that lend themselves to reproducible repeated measurements. It may be the case that, on occasion, the largest lesion does not lend itself to reproducible measurement in which circumstance the next largest lesion which can be measured reproducibly should be selected. A sum of the diameters (longest for non-nodal lesions, short axis for nodal lesions) for all target lesions will be calculated and reported as the baseline sum diameters. If lymph nodes are to be included in the sum, then only the short axis is added into the sum. The baseline sum diameters will be used as reference to further characterize any objective tumor regression in the measurable dimension of the disease.

9.7 Non-target Lesions

All other lesions (or sites of disease) including any measurable lesions over and above the 5 target lesions should be identified as non-target lesions and should also be recorded at baseline. Measurements of these lesions are not required, but the presence, absence, or in rare cases unequivocal progression of each should be noted throughout follow-up.

9.8 Evaluation of Target Lesions

NOTE: In addition to the information below, also see section 4.3.2 in the international criteria proposed by the Response Evaluation Criteria in Solid Tumors (RECIST) Committee, version 1.1 (Eur J Cancer 45;2009:228-247) for special notes on the assessment of target lesions.

Complete Response (CR)	Disappearance of all target lesions. Any pathological lymph nodes (whether target or non-target) must have reduction in short axis to <10 mm.
Partial Response (PR)	At least a 30% decrease in the sum of the diameters of target lesions, taking as reference the baseline sum diameters
Progressive Disease (PD)	At least a 20% increase in the sum of the diameters of target lesions, taking as reference the smallest sum on study (this includes the baseline sum if that is the smallest on study). In addition to the relative increase of 20%, the sum must also demonstrate an absolute increase of at least 5 mm. (Note: the appearance of one or more new lesions is also considered progressions).
Stable Disease (SD)	Neither sufficient shrinkage to qualify for PR nor sufficient increase to qualify for PD, taking as reference the smallest sum diameters while on study

9.9 Evaluation of Non-target Lesions

Complete Response (CR)	Disappearance of all non-target lesions and normalization of tumor marker level. All lymph nodes must be non-pathological in size (<10 mm short axis) Note: If tumor markers are initially above the upper normal limit, they must normalize for a subject to be considered in complete clinical response.
Non-CR/ Non-PD	Persistence of one or more non-target lesion(s) and/or maintenance of tumor marker level above the normal limits
Progressive Disease (PD)	Appearance of one or more new lesions and/or unequivocal progression of existing non-target lesions. Unequivocal progression should not normally trump target lesion status. It must be representative of overall disease status change, not a single lesion increase.

9.10 Evaluation of Best Overall Response

Target Lesions	Non-Target Lesions	New Lesions	Overall Response
CR	CR	No	CR
CR	Non-CR/ Non-PD	No	PR
CR	Not evaluated	No	PR

Target Lesions	Non-Target Lesions	New Lesions	Overall Response
PR	Non-PD/ or not all evaluated	No	PR
SD	Non-PD or not all evaluated	No	SD
Not all evaluated	Non-PD	No	Non-evaluable
PD	Any	Yes or No	PD
Any	PD*	Yes or No	PD
Any	Any	Yes	PD

*In exceptional circumstances, unequivocal progression in non-target lesions may be accepted as disease progression.

Subjects with a global deterioration of health status requiring discontinuation of treatment without objective evidence of disease progression at that time should be classified as having “symptomatic deterioration”. Every effort should be made to document the objective progression even after discontinuation of treatment.

9.11 Imaging biomarkers: Bone

Record changes on bone scan as improved or stable (no new lesions) or worse (new lesions). Changes in intensity of uptake do not constitute progression or regression. For progression to occur, at least two new lesions must appear on first post-treatment scan, with at least two additional lesions on the next scan at least 6 weeks later (2+2 rule). If at least two additional lesions are seen on the next (confirmatory) scan, the date of progression is the date of the first scan, when the first two new lesions were documented. For all scans after the 12 week scan, at least two new lesions indicates progression. Date of progression is the date of the scan that first documents the second lesion.

9.12 Blood-based marker: PSA

Record the percent change from baseline at 12 weeks, and separately, the maximal change at any time. PSA at twelve weeks will be used to determine response. PSA decrease of 50% or more will be counted as PSA response. PSA increase of 25% or more will be counted as PSA progression.

10. DRUG INFORMATION

10.1 Ipatasertib

Ipatasertib is an AKT inhibitor that acts by binding to the adenosine triphosphate (ATP)-binding pocket of the activated isoforms of AKT.

Please refer to the current version of the Investigator's Brochure (IB) for additional information regarding this drug.

10.1.1 Supplier/How Supplied

The Ipatasertib Drug Product will be supplied by Genentech, Inc. at no charge to subjects participating in this clinical trial as 100- and 200-mg tablets.

The investigator shall take responsibility for and shall take all steps to maintain appropriate records and ensure appropriate supply, storage, handling, distribution, and usage of investigational product in accordance with the protocol and any applicable laws and regulations.

10.1.2 Preparation

Ipatasertib is provided as oral tablets.

10.1.3 Storage and Stability

Ipatasertib should be stored at room temperature.

10.1.4 Handling and Disposal

Ipatasertib should be handled in accordance with good practice rules and local guidelines for oral anticancer drugs.

After final drug reconciliation, unused ipatasertib should be disposed at the site following procedures for the disposal of anticancer drugs.

10.1.5 Dispensing

Ipatasertib must be dispensed only from official study sites and to eligible subjects under the supervision of the site investigator. Ipatasertib should be stored in a secure area according to local regulations. It is the responsibility of the site investigator to ensure that study drug is only dispensed to subjects.

10.1.6 Adverse Events

Adverse events associated with ipatasertib use include diarrhea, nausea, vomiting, alopecia, neuropathy, fatigue, rash and decreased neutrophil count. Please refer to the IB for the comprehensive list of adverse events associated with ipatasertib use.

10.2 Darolutamide

Darolutamide is an androgen receptor inhibitor that competitively inhibits androgen binding, nuclear translocation and androgen receptor mediated transcription.

Please refer to the latest version of the prescribing information that can be found at <http://www.accessdata.fda.gov/scripts/cder/drugsatfda/>, and/or on the manufacturer's website.

10.2.1 Supplier/How Supplied

Darolutamide will be supplied by Bayer at no charge to subjects participating in this clinical trial.

The investigator shall take responsibility for and shall take all steps to maintain appropriate records and ensure appropriate supply, storage, handling, distribution, and usage of investigational product in accordance with the protocol and any applicable laws and regulations.

10.2.2 Preparation

Darolutamide is provided as oral tablets.

10.2.3 Storage and Stability

Store at 20°C to 25°C (68°F to 77°F); excursions permitted between 15°C and 30°C (59°F and 86°F).

10.2.4 Handling and Disposal

Darolutamide should be handled in accordance with good practice rules and local guidelines for oral anticancer drugs.

After final drug reconciliation, unused darolutamide should be disposed at the site following procedures for the disposal of anticancer drugs.

10.2.5 Dispensing

Darolutamide must be dispensed only from official study sites and to eligible subjects under the supervision of the site investigator. Darolutamide should be stored in a secure area according to local regulations. It is the responsibility of the site investigator to ensure that study drug is only dispensed to subjects.

10.2.6 Adverse Events

Adverse events associated with darolutamide include fatigue, pain in an extremity, rash, ischemic heart disease and heart failure. Please refer to the package insert for darolutamide for the comprehensive list of adverse events associated with darolutamide use.

11. ADVERSE EVENTS

11.1 Definitions

11.1.1 Adverse Event (AE)

An AE is any untoward medical occurrence whether or not considered related to the study drug that appears to change in intensity during the course of the study. The following are examples of AEs:

- Unintended or unfavorable sign or symptom
- A disease temporally associated with participation in the protocol
- An intercurrent illness or injury that impairs the well-being of the subject

Abnormal laboratory values or diagnostic test results constitute AEs only if they induce clinical signs or symptoms or require treatment or further diagnostic tests.

Hospitalization for elective surgery or routine clinical procedures that are not the result of an AE (e.g., surgical insertion of central line) should not be recorded as an AE.

Disease progression should not be recorded as an AE, unless it is attributable to the study regimen by the site investigator.

